Data Analysis Plan. SPM12 ⁵⁵ will be used for fMRI statistical analyses. EPI time series' preprocessing will include: (1) realignment for motion correction, (2) slice timing correction, (3) co-registration of EPI with anatomical data, (4) spatial normalization to MNI anatomical, and (5) spatial smoothing. Head motion outliers in EPI time series will be corrected using the Artifact Detection Tools with a scan-to-scan movement threshold of 0.2 mm and a scan-to-scan global signal change of 3 SD ⁵⁶. Activity. For each subject, BOLD activity contrast signal variance will be modeled with regressors using a General Linear Model (GLM) to generate 1st level contrasts (NF vs. CB and NF vs. Rest) for the ESF-NF task similar to procedures followed by Young et al. ³². [name] will lead activity analyses. Connectivity. Time series in dACC or right-amygdala for the ESOM and ER tasks will be used to yield general psychophysiological interaction (gPPI) contrast variables ⁵⁷. The gPPI variables represent FC differences for 'self' vs. 'other' faces recognition or 'regulation' vs. 'passive' viewing. The processing pipeline configuration will be available online. The research staff and a software programmer will generate automatic pre-processing scripts using pilot adult data to yield 1st level images for both activity, connectivity, and structural data to ensure rapid quality control and data access. General PPI analyses yield information flow between neural nodes without direction of exchange. Competing models of affect valuation versus affect modulation/suppression assume 'bottom-up' influence from amygdala on mPFC or 'top-down' influence from the mPFC and dACC on the amygdala, respectively⁵⁸. Dynamic causal modeling (DCM)⁵⁹⁻⁶¹ will follow up gPPI analyses to test bottom-up vs. top-down models of information flow between target neural hubs. DCM will also test FC patterns during NF training but increase target activity during NF is the key target for our Milestone 1. [name] will conduct FC analyses and determine how functional neuro-architecture of affect regulation and self-processing changes after NF training. Defining ROIs. In line with our focus on amygdala, dACC, and their connectivity with mPFC, we will target the dACC (MNI: x=-8, y=30, z=30), the highest loci of activity within the ACC in our pilot results and the right amygdala (MNI x=28 y=0 z=-19), the loci of our amygdala-ACC FC results in attempting participants ⁴¹. ROIs of activity (5 mm) centered in those coordinates during NF, and their FC to mPFC (polar aspects of BA10-9) during ER and ESOM tasks are the target ROIs. The unrelated locus is the left horizontal segment of the intraparietal sulcus (MNI x=-42 y=-48 z=48). This region is not involved in emotion regulation or self-processing and has been used before as a locus of Unrelated comparison NF ^{32,34-36}. Finally, our decision of using specific coordinates, instead of localizing ROIs with a task that elicits dACC or amygdala activity, is supported using pre-determined coordinates for NF in research that yielded ROI up-regulation and symptoms improvement ^{32,34-36}. Accordingly, we have selected coordinates based on our published and pilot work. Puberty ⁵¹, illness or depression (BDI) severity, treatment indexes, substance use, IQ, handedness, or any variable differing between key groups will be covariates in all analyses.

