be performed on 1st-level gPPI contrast images⁶² representing FC estimates for ‘self’ vs. ‘other’ faces recognition and for ‘regulate’ vs. ‘passive’ viewing conditions (with similar thresholds as above). Right-amygdala or dACC to mPFC FC will be tested with 1st level gPPI maps in mixed-effects analysis-of-variance (ANOVA) with time as within-group effects (Pre- and Post-NF training) to model FC parameters and compute effect sizes⁵⁷. In a follow-up DCM analyses we will test for direction of information flow between hubs identified with gPPI analyses. Models for all plausible configurations of causal information exchange between two neural nodes (amygdala or dACC and mPFC) will be defined. The ESOM and ER task conditions are assumed to drive causal information flow. Links with psychological targets: Amygdala and dACC to mPFC FC will be extracted and correlated with changes in psychological targets, i.e., emotion regulation and self-processing behavior in the ETB⁴⁰ and IAT^{38,39} before vs. after NF training. We will also test correlations with self-reported change (DERS, SPPA, RD) in those constructs²³⁻²⁵.

R33 Aim 1: Confirm target engagement in the NF versus the Unrelated-NF group.

H1.1: Right amygdala or dACC activity will be higher for active versus unrelated-NF. A Bayesian ANOVA model will be fit for each ROI, where the primary predictor for each model is the indicator for the NF group, which will quantify the difference in activity parameters between the NF and Unrelated-NF groups.

H1.2: Right amygdala or dACC – mPFC FC will be higher during self-processing and affect regulation tasks following active NF compared to Unrelated-NF training sessions. A Bayesian analysis-of-covariance (ANCOVA) will model how each of the FC parameters relate to each of the affect dysregulation and self-processing behavioral scores. The predictors will be the NF indicator terms, which will quantify how each of these scores are affected by NF, the main effect of the neural target, and the interaction term between main effect and NF indicator. This interaction term will measure the difference in the association between the neural targets and the behavioral scores between the NF and Unrelated-NF groups.

R33 Aim 2: Test the relationship between neuropsychological targets’ engagement and behavioral changes.

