H2.1: Lower affect dysregulation and abnormal self-processing behavior will follow active compared to Unrelated-NF, mediated by amygdala or dACC to mPFC FC changes in self-processing and affect regulation tasks. Bayesian mediation models will test the role of dACC or amygdala-mPFC FC changes on the relationship between NF and affect dysregulation and self-processing behaviors (ETB and IAT)⁶³. The outcome will be the behavioral change (ETB, IAT). The 1st linear model will be one used for H1.2, to test the relationship between the change in FC parameters and behaviors. For the 2nd linear model, the primary predictor will be the indicator term for the NF group, to establish the relationship between NF and behavioral change. Finally, in a 3rd model, the primary predictors will be indicator terms for the NF group, the change in FC parameters, and the interaction between them, to quantify the degree to which NF modifies the relationship between the change in FC parameters and behavioral change.

H2.2: Higher amygdala or dACC to mPFC FC after NF will be associated to lower suicide ideation. Bayesian linear model will use suicide ideation as the outcome, (C-SSRS, SIQ scores) and change in dACC or Amygdala-mPFC FC parameters in the ESOM and the ER tasks as the primary predictors.

H2.3: Affect dysregulation or abnormal self-processing behavioral changes will mediate the association between changes in FC and suicide ideation changes after versus before NF. Bayesian mediation models will test the direct and indirect effect of NF on suicide ideation, but this time we have two mediators: the neural targets and affect dysregulation or abnormal self-processing behavioral scores (ETB and IAT)^{63,64}. These mediators will interact, as we proposed in H2.1. We will fit a Bayesian mediation model with multiple mediators but this time with suicide ideation as the primary outcome, to quantify the direct and indirect effects of NF on suicide ideation change, with each of the change in FC parameters, affect regulation and self-processing behavior as potential mediators. We will fit another model that contains these mediation models as sub-models, i.e., a linear model with the NF indicator as primary predictor, each of the main effects for the change in FC and behavioral change, and an interaction term between the change in FC parameters and behavioral change.

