Bayesian Analyses in the R33 phase will use weakly informative priors using effects reported in the literature. Priors are a key strength of Bayesian models as they allow use of prior information to regularize models, e.g., using R61 phase results to adjust models in the R33 phase. This will boost statistical power since data from both phases will be used. Posterior distributions for model parameters will be constructed by combining priors with the likelihood function from the data. Markov Chain Monte Carlo (MCMC) procedures will be used to obtain samples from the posterior distributions for statistical inference. The Bayesian estimation will be implemented using custom R code in addition to the R package “BEST v0.4.0”^{65,66}.

Model selection and performance. In each of the Aims, we will start with baseline statistical model described above and improve the model by considering potential covariates that will allow the model to fit the data better and improve interpretability and predictive power. We will conduct a thorough search of potential statistical models that might improve on each of our baseline models. We will use residual analyses to assess how well each model fits the data and compute Bayes Factors to quantify quality of statistical models and use predictive cross-validation to assess the predictive capability of each model.

Data Integrity: The key scientific premise of this proposal is that improvement in emotion regulation and self-processing entail quantifiable changes in dACC and amygdala circuits. This proposal is aligned with the 2019 NIMH Strategic Plan 3.2: Develop ways to tailor new interventions to optimize outcomes and responds to the RFA MH-18-704: Development of Psychosocial Therapeutic and Preventive Interventions for Mental Disorders. Rigorous elements of the experimental design include: (a) using a specific threshold of

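### R33 H1.2 predicts higher connectivity after active NF, but its ANCOVA has behavior as outcome; no FC-outcome model is written out for R33 or linked to H1.2

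*Combined protocol and SAP*

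**What the plan says.** Section 1 (R33 Aim 1) and Section 18 both state H1.2 as a comparison of arms: "FC will be higher during self-processing and affect regulation tasks following active NF compared to Unrelated-NF training sessions". Section 18 then gives a Bayesian ANCOVA which "will model how each of the FC parameters relate to each of the affect dysregulation and self-processing behavioral scores". On its terms it says: "The predictors will be the NF indicator terms, which will quantify how each of these scores are affected by NF". The other two predictors are the main effect of the neural target and its interaction with NF. The interaction is described as the arm difference in the association between neural target and behavior.

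H1.1, immediately above, is written differently. Its NF indicator is the primary predictor, "which will quantify the difference in activity parameters between the NF and Unrelated-NF groups".

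H2.1 re-uses the H1.2 model and leaves no doubt about its direction: "The outcome will be the behavioral change (ETB, IAT). The 1st linear model will be one used for H1.2".

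FC is an outcome in one place in Section 18, the R61 milestone tests, which use a "mixed-effects analysis-of-variance (ANOVA) with time as within-group effects (Pre- and Post-NF training) to model FC parameters".

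**The concern.** R33 Aim 1 is to confirm target engagement, and H1.2 is its connectivity half. The written model answers another question: how behavior relates to FC and NF group. Its NF coefficient is an effect on behavior at a given level of FC. A result from it could be reported under H1.2 without saying whether training changed connectivity.

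The plan's model-building step adds to this. It starts from the baseline models as written and promises: "We will conduct a thorough search of potential statistical models that might improve on each of our baseline models". For H1.2 that baseline is the behavior model. The FC comparison would have to be taken from a mediation equation that is not written, or be specified later, possibly after the data have been seen.

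**Working it through.** The documents give no power, effect size or threshold for H1.2, so there is no figure to reproduce. The check is an inventory of the models in Section 18, followed by a short illustration.

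**Inventory**

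| Model | Outcome | Predictors |
|---|---|---|
| R61 FC ANOVA | FC | time (pre/post) |
| H1.1 | ROI activity | NF group |
| H1.2 | behavioral scores | NF, FC, NF x FC |
| H2.1, first | behavioral change | as H1.2 |
| H2.1, second | behavioral change | NF |
| H2.1, third | behavioral change | NF, FC change, NF x FC change |
| H2.2 | suicide ideation | FC change |
| H2.3, mediation | suicide ideation | NF, with FC change and behavior as mediators; mediator equations not written |
| H2.3, linear | not restated (taken as suicide ideation) | NF, FC change, behavioral change, FC change x behavioral change |

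The only row with FC as outcome is the R61 one, and R61 has no Unrelated-NF arm.

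**What each quantity is**

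- H1.2 concerns E[FC | active] - E[FC | unrelated].
- The ANCOVA models E[behavior | NF, FC] = b0 + b1 NF + b2 FC + b3 NF x FC. All its coefficients are conditional on FC, so the distribution of FC in each arm is not a parameter of the model.

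**Illustration**

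Input from the documents: 70 randomized 1:1 (Section 1), so 70/2 = 35 per arm. Assumptions: unit SDs, least squares in place of the Bayesian fit, two-sided 5%. Data were generated as FC = a NF + e1 and behavior = b FC + c NF + i NF x FC + e2, and the written model was fitted in 20,000 trials per scenario.

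With b = 0.5, c = 0, i = 0:

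| Shift in FC, a (SD) | Mean NF term | NF term significant |
|---|---|---|
| -0.4 | 0.002 | 4.7% |
| 0 | -0.003 | 4.9% |
| 0.4 | 0.000 | 4.9% |
| 0.7 | 0.001 | 5.2% |

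The FC coefficient averages 0.50 and the interaction 0.00 at every shift, so nothing in the output tracks a.

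Three further cases:

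- **FC shifted by 0.8 SD, no FC-behavior link (4,000 trials).** All three ANCOVA coefficients average within 0.003 of zero. Regressing FC on NF group recovers 0.797.
- **FC not shifted, direct effect c = 0.5 on behavior (b = 0.5).** The NF term averages 0.502 and is significant in 53.2% of trials, although H1.2 is false.
- **True interaction, mean-centered FC, c = 0.** The NF term has expectation i x a/2. With a = 0.4 and i = 0.7 this is 0.7 x 0.4/2 = 0.14 (simulated 0.138); with i = -0.7 it is -0.14 (simulated -0.143). The same rise in FC gives opposite signs.

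**The case against.** The best defense is that the comparison is present elsewhere. H2.3 asks for direct and indirect effects of NF on suicide ideation with FC change as a mediator, and an indirect effect through FC cannot be computed without an NF-to-FC path. H2.1 implies the same path. This stands in part. A reader might infer from the H1.2 mismatch that no R33 analysis would estimate the arm difference in FC at all; the documents do not support that. They do not, however, write the path as an equation, give it covariates or a baseline, or present it as the test of H1.2.

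A second defense is that H1.1 is fitted for each ROI, and the ROI definition in Section 18 mentions FC to mPFC. This does not rescue H1.2, because the H1.1 model is expressly limited to activity parameters.

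A third is that R33 proceeds only if the R61 milestones are met, so there is time to repair the plan. That is true. It makes the repair cheap but does not supply the missing model.

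**Conclusion.** The concern holds as stated in the heading: the model written for H1.2 does not test H1.2, and no R33 model is written out with FC as outcome or linked to that hypothesis. This rests on the text alone. The simulated figures illustrate the consequence under assumed unit SDs, least squares and a 5% threshold; the Bayesian plan states no threshold. They are not needed for the conclusion. The H1.2 model should be corrected before R33 analysis begins.

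Two lesser points in Aim 2 need clarifying:

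- All three models listed for H2.1 have behavioral change as outcome, and the mediator equation is missing. The NF x FC term in the third is moderation and does not by itself test mediation.
- H2.3 says its mediators interact in the way set out for H2.1. The interaction in H2.1 is NF x FC, while the one H2.3 then writes is FC change x behavioral change.

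**What to change.** **H1.2.** For each task (ESOM, ER) and the seed chosen from R61, fit a Bayesian model with post-NF FC as outcome and NF group as primary predictor, adjusted for pre-NF FC and the Section 18 covariates ("IQ, handedness, or any variable differing between key groups will be covariates in all analyses" closes that list). Report the posterior of the NF coefficient as the test of H1.2. Move the present behavior ANCOVA to Aim 2.

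**H2.1 and H2.3 (clarification).** Write the mediator equation: FC change on NF group, adjusted for pre-NF FC. Label NF x FC as moderation, and reconcile the interaction H2.3 writes with the one it attributes to H2.1.

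Keep FC change, not post-NF FC, in outcome models that include NF x FC. The two give the same NF coefficient in a least-squares mediator equation that contains pre-NF FC, but they are not interchangeable in those outcome models. NF x change = NF x post - NF x pre, and the last term would be absent. With a true NF x FC-change interaction of 0.7 and a pre-post correlation of about 0.5, the fitted interaction averages 0.70 using change and 0.35 using post-NF FC. The second value agrees with 0.7 x (1 - 0.5) for equal pre and post variances.

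**Cost.** SAP wording and a few lines of model code. Table 1 already schedules both tasks before training at Visit 2 and after it at Visit 3, so no new scans, participants or procedures are needed.

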Milestone 1: NF loci (dACC or amygdala) must show higher activity during ESF-NF and higher FC with mPFC after NF training during the ESOM or ER tasks with effect sizes of $d \geq 0.4$.

Milestone 2: 20% of variance in psychological target's change (ETB, IAT) must be associated with amygdala or dACC to mPFC FC changes during the ESOM or ER tasks after NF.

If those milestones are met, during **the R33 phase**, 70 suicide attempting participants with pre-NF assessments will be randomized 1:1 to: NF or NF from a region that is not related to memory recall, labeled as "Unrelated-NF". Participants will be matched in sex, age, IQ, illness severity, suicide ideation, and abuse history if possible. Leveraging Bayesian methods to increase power, our aims and hypothesis (**H**) for the R33 phase are:

R33 Aim 1. Confirm target engagement in the NF versus the Unrelated-NF group.

H1.1: Right amygdala or dACC activity will be higher for active versus Unrelated-NF.

H1.2: Right amygdala or dACC – mPFC FC will be higher during self-processing and affect regulation tasks following active NF compared to Unrelated-NF training sessions.

R33 Aim 2. Test the relationship between neural and psychological targets' engagement and suicide ideation. H2.1: Lower affect dysregulation and abnormal self-processing behavior will follow active NF as compared to Unrelated-NF, mediated by amygdala or dACC to mPFC FC changes in self-processing and affect regulation tasks. H2.2: Higher amygdala or dACC to mPFC FC after NF will be associated with lower suicide ideation. H2.3: Affect dysregulation or abnormal self-processing behavioral changes will mediate the association between changes in FC and suicide ideation before versus after NF.

2. Background

Suicide is the 2nd leading cause of adolescent death in the U.S ²¹. Yet it is increasingly acknowledged that current evidence-based interventions for illnesses linked to suicide ideation and attempts underperform across the lifespan ^{1-7,22}.

3. Study Endpoints/Events/Outcomes

3.1 Primary Endpoint/Event/Outcome:

The primary outcome of the R61 stage will be the fMRI imaging results, behavioral tasks (IAT and EBT) and self-reported suicide ideation data. The DERS²³, RD¹²⁰ and the SPPA^{24,25} will provide self-report measures of affect dysregulation and abnormal self-processing. **The primary outcomes of the R33 stage** are similar as above but now include the C-SSRS⁹⁸ and SIQ²⁹ to test changes in suicide ideation and attempts

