25.9 Adults Unable to Consent: NA

Adolescent participants aged 18+ that are not able to consent or that demonstrate lack of understanding of research via the UBACC will be excluded or staff will endeavor to correct their understanding of research versus clinical provision of services and other characteristics of research endeavors.

26. Setting

26.1 Research Sites:

Participants will be identified in in-patient units and emergency rooms around the Twin Cities, including those in the Fairview U of M Clinic. Research procedures will be conducted at the U of M center for magnetic resonance research (**CMRR**) and at the U of M department of psychiatry.

26.2 International Research:

- NA

27. Multi-Site Research

- NA

28. Coordinating Center Research

28.1 NA

29. Resources Available

29.1 Resources Available:

During the 2-year R61 phase, we anticipate screening ~120 participants using standard MRI eligibility questions and screening for suicide ideation and attempts. A minimum of 56 participants will undergo baseline tests and pre- NF training tasks over 2 years. Historically, we have obtained fMRI and structural data with stringent criteria of signal-to-noise ratio and movement (i.e., displacement <0.2 mm) in ~90 % of participants in the target age range and disorders. Some attrition is expected due to movement and treatment discontinuation. We anticipate garnering good quality scans for all NF sessions in ~50 participants over 2 years randomly assigned to dACC or Right-Amygdala NF-Training. We budgeted for additional repeat scans to recover lost data if needed. We expect that 40 participants will complete all post-NF assessments and 1-month follow-up assessment, yielding 20 data sets per NF target with high quality scans and pre and post NF training data in the R61 phase.

We anticipate screening ~290 contacts for MRI eligibility over 3 years in the R33 phase. We expect to perform 100 baseline evaluations and pre-treatment tasks and to garner ~90 high quality scans for all NF sessions randomly assigned to active (dACC or Right-Amygdala depending on research phase) versus Unrelated-NF. Of those we anticipate at least 72 will complete the post-NF training phenotyping and 1-month follow-up. We have budgeted for repeat scans per year to obtain 70 complete pre and post NF-training phenotypical data and high-quality NF scans.

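### H2.1 analyses IAT and ETB as raw change without prespecifying the same task's pre-NF score as a covariate, which gives up precision on the arm effect

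*Combined protocol and SAP*

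**What the plan says.** Section 18, R33 Aim 2, H2.1 sets the outcome: "The outcome will be the behavioral change (ETB, IAT"). The arm effect is the second of three linear models: "For the 2nd linear model, the primary predictor will be the indicator term for the NF group". The third model contains the NF indicator, the change in functional connectivity (FC) and their interaction. The first is taken over from H1.2: "A Bayesian analysis-of-covariance (ANCOVA) will model how each of the FC parameters relate to each of the affect dysregulation and self-processing behavioral scores". The predictors listed there are NF, the neural target and their interaction. Despite the label ANCOVA, the covariate is the neural target and not the baseline task score.

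Two general rules in section 18 bear on covariates. The data analysis plan lists puberty, illness or depression severity, treatment, substance use, IQ and handedness, and ends "or any variable differing between key groups will be covariates in all analyses". The paragraph on model selection allows the team to "improve the model by considering potential covariates that will allow the model to fit the data better and improve interpretability and predictive power". Neither names baseline IAT or ETB.

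Section 3.1 counts the two tasks among the R61 primary outcomes and says that the R33 outcomes are similar. Table 1 schedules both at Visits 1, 4 and 5. The Visit 1 cell also lets them be given on either scan day, including once scanning on the second day is over. Section 1 gives the R33 size: "70 suicide attempting participants with pre-NF assessments will be randomized 1:1 to" active or Unrelated NF.

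**The concern.** A change score subtracts the whole baseline value, noise included. Regression on baseline subtracts only the part that predicts the later score. IAT and ETB yield reaction-time, accuracy and recall scores, whose test-retest correlation may be only moderate. With equal SDs and r below 0.5, change is less precise than ignoring baseline altogether. At stake is the width of the intervals for outcomes that the protocol counts as primary, in a trial of 70. The same change score is also the outcome in the mediation models.

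The two routes by which the baseline score might enter are weak. Adjustment triggered by an observed difference is not prespecified, and the gain in precision exists even when the arms are balanced. A model search chooses covariates after the data have been seen.

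**Working it through.** **Inputs from the documents.** 70 participants, 1:1, so 35 per arm (section 1). Section 29.1 says "Of those we anticipate at least 72 will complete the post-NF training phenotyping and 1-month follow-up" and aims for 70 complete data sets, so no further dropout is applied. There is no R33 power, alpha or precision figure to reproduce; R33 inference is Bayesian.

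**Inputs assumed.** Pre-post correlation r; the ratio k of baseline SD to post SD (k = 1 first); no other covariates. For the power illustration: an arm difference of 0.6 post-score SD and two-sided 0.05.

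**Variance per participant, in units of the post-score variance.**
- Change score: 1 + k² - 2rk, which equals (1 - r²) + (k - r)². With k = 1 this is 2(1 - r).
- ANCOVA: 1 - r².
- Information lost by change: 1 - (1 - r²)/(1 + k² - 2rk). With k = 1 this is (1 - r)/2.

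Since (k - r)² cannot be negative, ANCOVA is in large samples at least as precise for every r and k. The direction therefore does not depend on the assumptions; the size does.

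**Equal SDs.**

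| r | Var, change | Var, ANCOVA | Loss | 70 by change are worth | Power, change | Power, ANCOVA |
|---|---|---|---|---|---|---|
| 0.3 | 1.40 | 0.91 | 35% | 45.5 | 55% | 74% |
| 0.5 | 1.00 | 0.75 | 25% | 52.5 | 70% | 82% |
| 0.7 | 0.60 | 0.51 | 15% | 59.5 | 89% | 93% |

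The fifth column is 70 × (1 - loss). Power is from the non-central t with 35 per arm. At the ends of a wider range the loss is 50% at r = 0 and 5% at r = 0.9.

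**Unequal SDs.**
- k = 0.8: change variance 1.16, 0.84, 0.52 at r = 0.3, 0.5, 0.7; loss 21.6%, 10.7%, 1.9%.
- k = 1.25: change variance 1.8125, 1.3125, 0.8125; loss 49.8%, 42.9%, 37.2%.

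**Small-sample cost of estimating the slope.** The ANCOVA variance rises by a factor of about 1 + 1/(70 - 4), or 1.5%. Simulation with 35 per arm and equal SDs (10,000 trials) gave losses of 33.0%, 24.1% and 14.0% at r = 0.3, 0.5, 0.7. With equal SDs the cost cancels the gain only when (1 - r)/2 is near 1.5%, that is r near 0.97.

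**Chance imbalance.** One standard error of the baseline difference is √(2/35) = 0.24 SD. Given such a difference and k = 1, an unadjusted change-score contrast shifts by (1 - r) × 0.24: 0.17, 0.12 and 0.07 SD at r = 0.3, 0.5, 0.7. Adjustment for the baseline score removes this shift.

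**The case against.** The strongest reply is that the baseline score is not excluded. A primary predictor need not be the sole predictor, the covariate rule brings in any variable that differs between groups, and the model-selection paragraph allows more. This stands in part. A reader might infer that the plan rules baseline out, or leaves a visible imbalance uncorrected; the text supports neither. It supports only that the baseline score is not prespecified.

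A reader might also infer that the second H2.1 model is the only randomised comparison of the behavioural scores. It is not: H1.2 has NF terms for those scores too. That model conditions on the neural target and names no baseline score, so it does not close the gap.

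Third, randomisation makes the change-score contrast unbiased. That stands, and it makes this a question of precision rather than validity.

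Fourth, the size is unknown. The required covariates, such as BDI severity, may correlate with the baseline score and change the loss. The frequentist power figures are illustrations and not properties of the Bayesian plan. Both points stand. Weakly informative priors do not replace an omitted predictor, however, because the residual variance in the likelihood is the same.

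Finally, adjustment is not safe with just any Visit 1 score. Table 1 allows a first IAT/ETB after NF. Adjusting for such a score could remove part of the arm effect, and a change from it is no better founded.

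**Conclusion.** The point holds as a free improvement. H2.1 analyses IAT and ETB as change and does not prespecify the pre-NF score of the same task. ANCOVA would be at least as precise for any correlation and SD ratio, apart from a cost of about 1.5% in variance at this size.

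Under assumed r of 0.3 to 0.7 the loss is 35% to 15% with equal SDs, about 22% to 2% if the baseline SD is 0.8 of the post SD, and about 50% to 37% if it is 1.25 times. None of these is a figure from the documents. A reader might take 15% to 35% as an established loss of R33 information. The documents do not support that: they give no correlation or SD, and the loss concerns only the arm effect on IAT and ETB. It says nothing about activity during NF (H1.1), the FC contrasts or suicide ideation.

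**What to change.** - In every H2.1 model with a behavioural outcome, including the one reused from H1.2, prespecify the pre-NF score of the same task (IAT, or the particular ETB measure) as a covariate, whether or not the arms differ on it. Regressing the post score or the change on it gives the same arm estimate, so the change wording can stay if preferred.
- Name the post-NF visit used; IAT and ETB are scheduled at both Visit 4 and Visit 5.
- Use as baseline only a score obtained before the first NF run, and reconcile this with the Table 1 allowance for testing on the second scan day. A change score needs the same condition.

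The cost is a few lines of SAP text and one degree of freedom per model, negligible unless r is very high. No assessment is added. The FC-change mediator is a separate question that this does not settle.

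### H2.1 is stated as mediation, but its listed models describe effect modification, none models FC by arm, and no indirect effect or criterion is defined

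*Combined protocol and SAP*

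**What the plan says.** Section 18, R33 Aim 2, H2.1 states that lower affect dysregulation and less abnormal self-processing will follow active NF, "mediated by amygdala or dACC to mPFC FC changes in self-processing and affect regulation tasks". The named method is mediation: "Bayesian mediation models will test the role of dACC or amygdala-mPFC FC changes on the relationship between NF and affect dysregulation and self-processing behaviors", with a methods reference. The outcome is then fixed: "The outcome will be the behavioral change (ETB, IAT"). Three linear models follow.

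- **Model 1.** "The 1st linear model will be one used for H1.2, to test the relationship between the change in FC parameters and behaviors". Under H1.2 the predictors are the NF indicator, the neural target and their product, and the behavioural scores are what is predicted. Of the product it says: "This interaction term will measure the difference in the association between the neural targets and the behavioral scores", compared between the two arms.
- **Model 2.** "For the 2nd linear model, the primary predictor will be the indicator term for the NF group"; this relates arm to behavioural change.
- **Model 3.** Behavioural change on arm, FC change and their interaction, "to quantify the degree to which NF modifies the relationship between the change in FC parameters and behavioral change".

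H2.3, which has suicide ideation as outcome, does speak of direct and indirect effects of NF, and refers back to the interaction proposed in H2.1. Section 1 sets the R33 sample at 70, randomised 1:1. Section 18 plans posterior inference with weakly informative priors and gives no decision threshold for H2.1.

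**The concern.** Mediation and effect modification are different questions. Mediation asks whether NF moves FC and whether that movement carries the effect on behaviour. Modification asks whether the FC-behaviour slope differs between arms. Either can be present without the other. A mediation claim needs the arm-to-FC path, the FC-to-behaviour path, and a quantity that combines them. H2.1 describes the second path and a slope difference, and nothing that combines the paths.

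At stake is how the R33 result on mechanism will be read. Section 18 also allows a broad search for better-fitting models from each baseline model. With no defined estimand or criterion, what counts as support for H2.1 would be settled after the data are seen. H2.3 builds on the same structure.

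**Working it through.** **1. Is the arm-to-FC path modelled anywhere in R33?** Going through section 18:

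| Analysis | Outcome | Role of FC |
|---|---|---|
| H1.1 | ROI activity | none |
| H1.2 | behavioural scores | predictor |
| H2.1, models 1 to 3 | behaviour | predictor (1, 3) or absent (2) |
| H2.2 | suicide ideation | predictor |
| H2.3 | suicide ideation | mediator, no equation given |

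H1.2 is worded as an NF effect on FC, but the ANCOVA described for it predicts behaviour. The mixed ANOVA that does have FC as outcome belongs to the R61 milestones and names only time (before, after) as its effect. Models 1 and 3 have the same three terms.

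**2. What the interaction measures.** Write M = a·arm + e for FC change and Y = c·arm + b·M + i·arm·M + e for behavioural change. Model 3 is described as quantifying i. Under linear mediation i = 0 while a·b is not zero. Under pure modification a = 0 while i is not zero. So i on its own says nothing about a.

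**3. Size.** The documents give no effect sizes, power or threshold for H2.1, so there is no stated figure to reproduce. Assumptions: 35 per arm, unit residual SDs, flat priors, 95% interval excluding zero, c = 0. Simulated detection rates:

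| Scenario (assumed) | Interaction i | a·b, no interaction term | a·(b+i), interaction kept |
|---|---|---|---|
| Mediation, a = 0.8, b = 0.4 | about 5% | about 82% | about 58% |
| Mediation, a = 0.5, b = 0.4 | about 5% | about 48% | about 32% |
| Modification only, a = 0, i = 0.6 to 1.0 | about 64% to 97% | about 0% to 6% | about 0% to 6% |

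**4. Hand check by normal approximation.**

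- SE(a) = √(2/35) = 0.239. Detection of a: Φ(0.8/0.239 − 1.96) = 0.92 and Φ(0.5/0.239 − 1.96) = 0.55.
- Pooled slope: SE(b) = 1/√70 = 0.120, so Φ(0.4/0.120 − 1.96) = 0.92. Joint detection is 0.92 × 0.92 = 0.84 and 0.55 × 0.92 = 0.51.
- With the interaction kept, b + i is the slope in the 35 active-arm participants alone: SE = 1/√35 = 0.169, so Φ(0.4/0.169 − 1.96) = 0.66. Joint detection is 0.92 × 0.66 = 0.60 and 0.55 × 0.66 = 0.36.
- Interaction: SE(i) = √(2/35) = 0.239, so Φ(0.6/0.239 − 1.96) = 0.71 and Φ(1.0/0.239 − 1.96) = 0.99.

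These lie slightly above the simulated values, as expected of a normal approximation at this size. They also show why keeping the interaction costs power: the slope then comes from half the sample.

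**5. Change score against baseline adjustment.** With equal variances and pre-post correlation r, the change score has variance proportional to 2(1 − r) and the baseline-adjusted score to 1 − r². The ratio is (1 + r)/2, which is 0.70 at r = 0.4 and 0.80 at r = 0.6 (r is assumed).

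**The case against.** The best defence is that the plan names Bayesian mediation models, cites a method, and under H2.3 speaks of direct and indirect effects in wording that suggests H2.1 is the one-mediator case. It nowhere says that the interaction is the criterion for H2.1. This stands. A reader might infer that true mediation will be missed and that modification will be reported as mediation. The documents do not support that as fact; both errors follow only if the interaction is taken as the test.

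A reader might also infer that no indirect effect could be obtained from the listed models. That goes too far. Model 2 gives the total effect and model 3 the direct effect. In linear models on the same data, the total minus the direct effect at the control-arm mean FC change equals (b + i) times the arm difference in FC change. The coefficients are there, but the plan never forms the difference or gives it an interval.

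Nor is the arm-by-FC term an error. It is legitimate in an outcome model and, when present, enters the natural indirect effect. The overlap of models 1 and 3 is redundancy. The 5% rate under linear mediation is by construction the test's error rate, because those data have no interaction. Finally, the documents do not rank H2.1 above H2.2 or H2.3.

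What the defence does not supply is a stated arm-to-FC model, a defined indirect effect, or a criterion for H2.1.

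**Conclusion.** The point holds in conditional form. As specified, H2.1 is a mediation hypothesis whose final model is described as effect modification, with no R33 model of FC by arm and no defined indirect effect or criterion. This is more than missing detail, because the one purpose stated for the final model answers a different question.

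The structural finding rests on the text alone. The error rates apply only if the interaction is read as the test of mediation. All detection figures rest on assumed effects, unit residual SDs, 70 participants, flat priors and a 95% interval rule, none of which the plan gives for H2.1 except the sample size. The gap between the two indirect-effect definitions (82% against 58%, or 48% against 32%) is large enough that the choice should not be left until after the data are seen.

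**What to change.** Before R33 data are analysed, rewrite the H2.1 paragraph as follows.

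1. Add a mediator model: post-NF FC on arm and pre-NF FC.
2. Keep one outcome model: behaviour on arm, FC, baseline FC and baseline behaviour, with arm-by-FC if wanted. Drop the duplicate model 1.
3. Judge H2.1 on the posterior of one prespecified indirect effect, with its criterion: a·b without the interaction, or the natural indirect effect with it.
4. Report the interaction separately as effect modification.
5. State the assumption of no unmeasured mediator-outcome confounding, since FC is not randomised.

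As a separate improvement at no cost, analyse the post-NF ETB and IAT scores adjusted for their pre-NF scores in place of raw change. Residual variance is then 20% to 30% lower at the assumed r of 0.6 to 0.4.

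The cost is SAP wording and one extra model in the same MCMC code. Table 1 already schedules ESOM and ER before NF at Visit 2 and after NF at Visit 3, and IAT and ETB at Visits 1 and 4, so no new data are needed.
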